5.6.7 Retention Strategies to Ensure Follow-up

We will leverage the long-established retention strategies at the research site to retain participants in this study. Participants will be closely tracked by a dedicated experienced team of dedicated staff to minimize missed visits and loss to follow-up at both the Uganda and Malawi sites. This will be done primarily calling participants by mobile phone and reminding/re-scheduling visits as appropriate. Our staff also works with home locators to conduct a home visit as needed. This approach has proven highly successful at the two sites with 2-year retention rates >95% at prior trials in the Uganda and Malawi sites.

6.0 DATA MANAGEMENT

Standard operating procedures will be developed for all data management activities to ensure consistency and quality of data. All questionnaires and other study implementation materials will be pre- tested and the necessary revisions made prior to implementation. Data for paper-based neurodevelopment assessments and questionnaires will originally be encoded from hard copies into the Research Electronic Data Capture (REDCap) system with double data entry and error checklist verification for quality control. REDCap is a web-based database creation, management and entry tool. REDCap's easy design environment allows quick creation of web-based databases and data capture forms with special features like ad-hoc reporting and scheduling. It is widely used in the academic research community: REDCap Consortium is a collaborative, international network of more than 1700 institutional partners in over 95 countries. REDCap was developed by staff at Vanderbilt University in 2004 in order to help researchers manage data for small/medium sized projects in a systematic manner (metadata defined, secure, audit trails, etc). The system is continually updated and enhanced by the Project REDCap team at Vanderbilt. This installation of REDCap will be provided by Michigan State University Biomedical Research Informatics Core (BRIC). REDCap is maintained by the IT staff at BRIC. Access to REDCap database will be password protected to ensure confidentiality. Performance-based measures data from Brain Powered Games (BPG) will be off-loaded from the training tablets directly to Michigan State University Games for Entertainment and Learning (GEL) Lab's server and from there to BRIC for data merge and management.

Data for all portions of the study will originally be encoded from hard copies into the REDCap database system by the data managers at the Uganda and Malawi project offices. Double data entry and error checklist verification for quality control will be performed for all electronic files at the same office. Hardcopies will be archived at the Uganda and Malawi offices in safe and secure locations in locked cabinets at all times. All database systems at our Malawi and Uganda project offices will be password protected and Personal Identifier Information (PID) matched to participant Study ID numbers will be kept and encrypted in a separate electronic file and kept secured separately in a different study file cabinet on site.

Monthly email communications with Michigan State University will include updated enrollment and admissions data to monitor study progress. At MSU, the Data Management group for the MSU Biomedical Research Informatics Center (BRIC) will assist in the set-up and securing of all of our study data using their internet-based RIX information management system. The capabilities of this center are described in the MSU Resources section. Password protected database files will be sent by e-mail to [name], [name] and [name] at Michigan State University.

We will be able to download our project datasets and data definition dictionary from the RIX system to make data available to other research groups. We will require a collaborative agreement from such groups before making

such datasets available, as approved through the Intellectual Property Office at Michigan State University. See <http://newsroom.msu.edu/site/indexer/3004/content.htm> for an overview of this office and http://oip.msu.edu/documents/CDA2001_002.pdf for an example of such an agreement. In addition, we will ask to have final approval of all publications from other research groups who include our study data. MSU also has a Clinical Translational Science Institute (CSTI) described in our resources section of this application that provides support for DSMP surveillance in a clinical trials study.

No interim analyses of data are planned, and the study will not be stopped based on any statistical rules. To ensure reliability of data entry, a random sample will be reviewed by the investigators, and the results compared with the information recorded on the data base program. An acceptable error rate is less than 0.3%, i.e., three per 1000 entries. During data collection, quality assurance reports will be prepared on a quarterly basis and reviewed by the investigators. The reports will inform the investigators about missing, invalid, and inconsistent data on selected key variables. Co-I [name] will oversee preparation of the reports.

7.0 STATISTICAL CONSIDERATIONS

7.1 Power and Sample Size Calculations

7.1.1 General Statistical Approach

This study will utilize an observational longitudinal design. The analyses will account for repeated measurements within a child using generalized estimating equations, and marginalization to the unique participant level. Because this design is observational, potential confounders will be adjusted for in the analyses, and will be minimized by matching on parity, age, and site. This study is comprised of three groups: 1) HIV infected, 2) HEU, and 3) HUU children.

7.1.2 Statistical Approach by Specific Aim

Statistical analysis for Aims 1& 2. So as not to have to rely on American norms for standardizing our gold standard measures, we will use a statistical technique for standardization described from our cerebral malaria longitudinal studies with these tests.⁶⁵ [name] will evaluate the concurrent validity by computing correlation coefficients of the BPG and “gold standard” measures at intake (see Table 3) at 1 and 7 months. Correlations will be classified as: very strong ($r \geq 0.8$), strong (r range 0.6-0.79), moderate (r range, 0.4-0.59), weak (r range, 0.20-0.39), and very weak (range: 0-0.19). We will summarize the sensitivity of the BPG-based vs gold standard measures to the proximal (HIV infection) and distal factors (SES, home environment, growth) using: 1) relative validity coefficient; 2) standardized effect size;⁶⁶⁻⁶⁹ 3) standardized response mean (SRM) and Guyatt’s SRM.^{66,67,69,70} Larger values of these summary statistics correspond to greater sensitivity or ability to discriminate known groups. Interpretations similar to Cohen’s effect sizes⁶⁸ will be considered (e.g. SRM: ≥ 1.0 : excellent; 0.80-0.99: good; 0.50-0.79: moderate; and < 0.5 : weak). We will evaluate the predictive validity of the BPG-derived measures in the LME model with the repeated gold standard measures at 1 and 7 months (6-month follow-up). Covariates will include the BPG static measure at intake (baseline) and 1 month (post-training BPG; time-varying covariate), time (1 and 7 months), other covariates (proximal and distal factors, Figure 1), and number of prior neuropsychological testing sessions.

Statistical analysis for Aim 3. Two sets of the LME models will be fit: one with 3 repeated “gold standard” measures, and one with 3 BPG-derived measures. To model potential non-linear patterns over time, we will enter time as a class variable with levels of intake, 1, and 7 months. Based on past experience, we expect gains in outcomes between intake and 1 month due to training, and a slower rate of change in the subsequent 6-month period with no training. Summary statistics for change over time for the gold standard vs BPG-derived measures will be compared as described under statistical analysis for Aim 1.

Sample sizes for Aims 1, 2, and 3. Sample size considerations are based on having sufficient power to discriminate known groups based on the proximal factor of HIV status/exposure, a key factor for Aim 1. The preliminary data from PROMISE ND study indicate that the differences in the composite neurodevelopmental score (the Mullen Scale of Early Learning) between HEU and HUU cohorts corresponded to the effect size of Cohen's $d=0.26$ (difference between the means of 0.26 of the standard deviation). To detect this difference between HUU and HEU cohorts, $n=240$ per cohort is needed for power ≥ 0.80 in two-tailed tests at 0.05 level of significance. Based on the preliminary data, the effect size d for comparisons of the HIV vs HUU or HEU is at least 0.31. This can be detected with power ≥ 0.80 with $n=120$ in the HIV group. Therefore, the proposed total sample size for both sites combined is $n=240$ HUU; $n=240$ HEU; and $n=120$ for HIV+ children.

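### Section 7.1.2 leaves open whether its weak-to-excellent bands cover the between-cohort effect size, and it gives no uncertainty for the comparison of BPG with the gold standards

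*Combined protocol and SAP*

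**What the plan says.** In section 7.1.2 (Aims 1 and 2) the sensitivity analysis is comparative: "We will summarize the sensitivity of the BPG-based vs gold standard measures to the proximal (HIV infection) and distal factors". Three kinds of statistic are listed: a relative validity coefficient, a standardized effect size, and the SRM with Guyatt's variant. The plan then says: "Larger values of these summary statistics correspond to greater sensitivity or ability to discriminate known groups". The next sentence gives the scale. It opens "Interpretations similar to Cohen’s effect sizes", says these will be considered, and prints bands with the SRM as the example: 1.0 or more is excellent, then "0.80-0.99: good; 0.50-0.79: moderate", and below 0.5 is weak. Correlations have their own bands. No other scale is given for the standardized effect size.

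The sample-size paragraph of the same section rests on known-groups discrimination: "Sample size considerations are based on having sufficient power to discriminate known groups based on the proximal factor of HIV status/exposure". For HEU v HUU it uses Cohen's d = 0.26 ("difference between the means of 0.26 of the standard deviation"), taken from "differences in the composite neurodevelopmental score (the Mullen Scale of Early Learning) between HEU and HUU cohorts". For the HIV+ cohort, the effect size for "comparisons of the HIV vs HUU or HEU is at least 0.31". The cohorts are 240 HUU, 240 HEU and 120 HIV+.

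**The concern.** The SRM is a within-child statistic: mean change divided by the SD of change. The effect sizes that set the sample size are cross-sectional differences between cohorts. The text does not say whether the bands belong to the first kind only or to both. The wording that leads into them (all the summary statistics, discrimination of known groups, Cohen's effect sizes) invites an analyst to use them for both.

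If they are used for both, the effects the study is powered to detect lie in the lowest band. BPG and a gold standard could both be called weak when they discriminate equally well, or when BPG discriminates better (0.4 against 0.26, say). The label then carries no information on the question the study asks, which is whether BPG is more sensitive than the existing tests.

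The statistics that do address that question are compared only by which is larger. Section 7 gives no interval or test for the contrast, so a chance difference between two values of d could be read as a difference in sensitivity.

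**Working it through.** **Inputs from section 7.1.2.** d = 0.26 with 240 v 240; d = 0.31 with 120 v 240; two-sided 0.05; power at least 0.80; weak means below 0.5.

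**Plan's own figures.** n per group = 2(1.960 + 0.842)²/0.26² = 233, and power at 240 is Φ(0.26/√(2/240) − 1.96) = 0.813. The stated 240 reproduces. For the HIV+ contrast, power is Φ(0.31/√(1/120 + 1/240) − 1.96) = 0.792. Power of 0.80 needs 123, so the stated 120 reproduces closely.

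**Chance of a weak label if the 0.5 cut is applied to d.** SE(d) = √(1/n₁ + 1/n₂ + d²/(2(n₁ + n₂))).

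- HEU v HUU: SE = √(0.008333 + 0.000070) = 0.0917. P(observed d < 0.5) = Φ((0.5 − 0.26)/0.0917) = 0.996; the noncentral t gives 0.995.
- HIV+ v either other cohort: SE = √(0.012500 + 0.000133) = 0.1124. P = Φ((0.5 − 0.31)/0.1124) = 0.954; the noncentral t gives 0.953.

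Dependence on the assumed true d (noncentral t):

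| True d | 240 v 240 | 120 v 240 |
|---|---|---|
| 0.26 | 0.995 | 0.983 |
| 0.31 | 0.980 | 0.953 |
| 0.40 | 0.86 | 0.81 |
| 0.50 | 0.50 | 0.50 |
| 0.60 | 0.14 | 0.19 |

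**The SRM.** No expected gain, SD of change or pre-post correlation is given, so the chance of a weak SRM cannot be computed. Assuming equal SDs before and after, SRM = g/√(2(1 − r)), where g is the gain in baseline SD units and r the pre-post correlation. The SRM reaches 0.5 at g = 0.59, 0.50, 0.39, 0.32 or 0.22 for r = 0.3, 0.5, 0.7, 0.8 or 0.9. Neither 0.26 nor 0.31 enters this.

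**Precision of the paired comparison.** Both tests are taken by the same children, so the two values of d are correlated. With equal standard errors and a within-cohort correlation ρ between BPG and the gold standard, SE(difference in d) ≈ SE(d) × √(2(1 − ρ)). The plan gives no expected ρ; 0.3 to 0.7 is assumed here.

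- HEU v HUU, ρ = 0.7: 0.0917 × 0.775 = 0.071, so the 95% CI is about ± 0.14.
- HEU v HUU, ρ = 0.3: 0.0917 × 1.183 = 0.108, about ± 0.21.
- HIV+ contrast: 0.1124 × 0.775 = 0.087 to 0.1124 × 1.183 = 0.133, about ± 0.17 to ± 0.26.

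For 80% power to show a difference in d between HEU and HUU, the true difference would have to be about 2.80 × 0.071 = 0.20 to 2.80 × 0.108 = 0.30. That is about as large as the cohort effects themselves.

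**The case against.** A reader might infer that BPG is almost certain to be graded weak even if the study goes as planned. The documents do not support that, for four reasons.

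- The printed bands name the SRM, and interpretations of this kind are only to be considered. No band is a success criterion. The primary outcome in section 5.3 is the correlation with the gold standards, which has separate bands.
- The 0.26 was seen on the Mullen, and 0.31 is a floor. They are differences the study should be able to detect; they are not predictions for BPG. Section 3.0 hypothesizes that dynamic BPG is more sensitive than the static tests.
- A reader might also infer that the cohorts alone fix d, so that any instrument would show 0.26 to 0.31. Observed d depends on the instrument, through measurement error and the domain tested. If it did not, comparing BPG with a gold standard would be pointless.
- The plan already sets BPG against the gold standards and lists relative validity.

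All four points stand, and they remove any claim about the study's overall result. Two gaps remain. The plan does not say which statistics the bands cover: on the narrow reading, the statistic that set the sample size has no interpretation rule, and on the wide reading it has an uninformative one. The comparison between instruments also has no stated uncertainty.

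**Conclusion.** The point holds as a conditional one, at low severity. If the bands are carried over to the between-cohort effect size and BPG's true d equals the planning values, a weak label is very likely (99.5% and 95%), and still 81-86% likely at d = 0.4. The condition matters: at a true d of 0.5 it is an even chance, and at 0.6 it is 14-19%. Nothing follows about the SRM, and no label determines whether BPG is judged valid.

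The more useful part concerns the comparison. Under the assumed correlations of 0.3 to 0.7, the difference in d between BPG and a gold standard has a standard error of about 0.07 to 0.11 for HEU v HUU. Against effects of 0.26 to 0.31 that is large, so ranking the instruments by point estimate could mislead.

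**What to change.** 1. State in section 7.1.2 that the weak-to-excellent bands apply only to within-child change (the SRM).
2. For known-groups sensitivity, report d for BPG, d for the KABC-II MPI and d for each of the other gold standards in the same children. Give the difference in d, or the relative validity coefficient, with a paired bootstrap 95% CI, resampling children within cohort so that each child's scores stay together.
3. Claim that BPG is more sensitive only if the interval excludes no difference.

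The data are already planned, so the cost is SAP wording and a little more analysis. The drawback is that the interval may be too wide to support a claim of superiority or of equivalence. An equivalence or non-inferiority margin could be added, but its value is debatable and the precision above may not support one, so it is not part of this recommendation.

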Figure 3. Using dynamic assessments in this proposal to test how BPG improves cognition in HIV+ school age children is supported by the recent results (presented above in 3A, 3B and 3C) of Duncan et al. (20), who show 24 sessions of CCRT training with COGMED strengthens cortical connectivity for working memory and attentional processes.

Our central hypothesis is that the performance gains (dynamic assessment) will explain the additional variation in the gold-standard measures at time points after static (baseline) assessment, and more effectively capture the effects of HIV/ARV exposure and treatment across our cohorts (HIV, HEU, HUU) in Uganda and Malawi.

Overall Impact: Once BPG is proven as a dynamic assessment tool, BPG mobile apps can be used in tablets and smart phones for “real-time” cognitive assessment monitoring (or surveillance) for HIV disease progression and treatment. BPG can also monitor other diseases causing brain/behavior problems in children.

BPG will be the first adapted and validated instrument for dual assessment capability, both static and dynamic. It will also be the first to include a static and dynamic intervention-based measured of executive function (EF) in

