side of Fig. 4 slope). Thus, dynamic measures over 12 sessions carry the same information as measures over all 24 sessions.

Table 1 shows correlations of CCRT performance gains with the KABC-II mental processing index (MPI) pre-training (Static Pre-) and post-training (Static Post-). Measures over first 12 sessions (4 weeks) had the same or stronger correlations with the KABC-II MPI, than measures based on 24 sessions (Dynamic), further confirming the adequacy of 12 sessions for dynamic measurement. To determine the value added by dynamic measures over existing static (Static Pre- or Post-) assessments, we used general linear models relating the KABC-II MPI post-training to the KABC-II MPI pre-training, and each dynamic performance measure (one at a time over each successive training session). While the KABC-II MPI at baseline was strongly associated with the KABC MPI post-training, the performance measures were significantly related to the KABC MPI post-training over and above baseline MPI (Dynamic column in Table 1), capturing variation in post-training KABC-II MPI not captured by the *Captain's Log* Static Pre- or Post- measures.

For children at each session, with consistent linear growth across all successive training sessions (Fig.4). Dynamic measures derived based on the first 12 sessions (left side of Fig. 4 slope) had the same rate of gains over time as measures across the final 12 sessions (right side of Fig. 4 slope).

(horizontal axis) as measured by CSF neuroinflammatory (TNF-alpha) and endothelial activation (von Willibrand Factor: vWF) during acute illness. The full CCRT (blue), limited CCRT (green) and control (red) arms are represented for the cerebral malaria (left side) and non-malaria (right side) cohorts. More severely affected children show poorer positive neuroplasticity in terms of CCRT learning benefit. We expect the same result for our HIV-affected cohorts, further showing the sensitivity of CCRT assessment measures.

Since the focus is on assessment as part of neurocognitive rehabilitation (CCRT), we propose that using computer games to provide for dynamic measures across 12 sessions is much more feasible, from the standpoint of disseminating BPG as an assessment and rehabilitative tool. Also, our initial pilot study with CCRT and Ugandan children with HIV had a significant gold standard test benefit across just 12 training sessions.⁵

Table 2. Results of CCTP Repeated Measures Analyses Severe Malaria Study

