5.0 NEURODEVELOPMENTAL ASSESSMENT PROTOCOL DESIGN

5.1 Overview of Study Design:

[figure not shown]
Static and Dynamic Assessment Process for Each Study Child. Figure 6 provides an overview of study visits and assessments. Following enrollment and physical and medical exams, each child will return to the clinic with their principal caregiver for a half-day of gold standard neuropsychological assessments (KABC-II, TOVA, CogState). At this time the caregiver will complete the Achenbach CBCL questionnaire for school-age children, the Caldwell HOME scale, the SES material possessions evaluation, and the Hopkins Symptom Checklist-25 (caregiver psychological well-being). We will explain assessments and provide instructions in the local language. Study assessments will proceed in two phases. In Phase I, children will be randomized to start BPG trainings (50% of sample) or to a wait-list condition. Within a week after baseline assessment, the full sample of children will be contacted by a field research assistant and facilitate a first BPG session. This first session will be completed by the full sample because it will be considered as an internal performance evaluation session with BPG and will be completed on a tablet, supervised by the field research assistant. This will be done as part of the 50-60 minutes training session on the 5 BPG games (about 10 minutes per game), and will constitute the BPG static assessment. Thereafter, the field research assistant will return with children allocated to the BPG trainings (50% of sample) at a convenient time and supervise BPG training several times per week until 12 training sessions are completed. The 12th session internal evaluation performance measures for the 5 core games and one added EF game will provide the endpoint for BPG dynamic assessment (gain in BPG performance from session 1 to session 12). Because BPG training will occur on a tablet connected to the internet through the mobile network, performance data can be uploaded for analysis via the MSU GEL lab principal server, as done in the Kayunga Uganda CCRT study with BPG ¹.

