5.6.5 Overview of Brain Powered Games

The BPG subtests were designed/selected based on what has been validated from the attention/working memory/visual-spatial categorization and analysis subtests validated in previous CCRT clinical trials work from BrainTrain Captain's Log ¹. However, Captain's Log was proprietary and not available for transition to scale for LMICs in Africa. Furthermore, it is no longer available or supported, and its successor has not been tested in Uganda. BPG is designed to address the very same cognitive skills as Captain's Log Uganda was, but is scalable, accessible and affordable for the African context. Additionally, BPG has been previously proven to improve neurocognition among Ugandan children with HIV¹⁸.

Each BPG game includes a visual tutorial, several adjustable settings on the administrative side (Admin), and records game play data for research purposes. As part of a current preliminary study using BPG with aging Ugandan adults with HIV, we have now adapted BPG as a mobile app for the touch screens of tablets and smart phones, as part of a preliminary study of BPG dynamic assessment in aging adult HIV patients in Uganda. Our preliminary findings thus far have documented that the neuropsychological gain scores from pre- to post-training with BPG are sensitive to the clinical and health parameters of our patients at enrollment, including ARV adherence, viral load, adverse health events, and CD4 nadir. We will also use gain scores pre- to post-training for our gold standard of neuropsychological tests as our principal performance outcomes in the present study, as noted in Table 3 (far right column) for each of the BPG training games below.

Butterfly. Here a butterfly flies across the screen and the child touches it when the butterfly stops moving. When the child touches the butterfly, the child earns 10 points, the butterfly moves somewhere else on the screen, and the process is repeated. The game continues until the child scores a set number of points. Butterfly serves as a training exercise, letting a child become familiar with the game interface on the tablet.

iSpy. This is a memory game. iSpy shows the child a scene with several objects. After a few seconds in which the child is supposed to memorize the objects, iSpy removes the scene. A few seconds later the scene reappears — but now with a new object. The child must recall which objects were in the previous scene

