5.6.6 Summary of Procedures by Study visit

The following procedures will be conducted at the screening and enrollment visit of all enrollees

Table 1: Enrollment and Intake Visit(s) for all enrollees

Component	Procedures
Administrative and Regulatory	
 • Assess eligibility • Obtain written informed consent/ assent • Assign a Participant Identification (PTID) Number • Provide reimbursement for study visit
Clinical	
 • Obtain medical history • Conduct a brief physical examination (main organ systems and
Neurodevelopment Assessments	KABC-II TOVA
Caregiver-reported assessments	CBCL HOME
Brain Powered Games	1 st session for treatment condition (e.g. training) and only 1 session for wait list group (e.g. assessment)

*Depending on staff availability and scheduling, enrollment and baseline visits will be done on the same day

Table 2: BPG training visits for 50% of sample

Component	Procedures
Administrative and	
 • Schedule next visit
Brain Powered Games package	
 • Complete 10 sessions (About 2 per week for 6 weeks) of approximately 30-45 min

Table 3: Follow-up Visits for all enrollees

Component	Procedures
Administrative and	
 • Provide reimbursement for study visit

Clinical	
 • Obtain medical history • Conduct a brief physical examination (main organ systems and
Neurodevelopment Assessments	KABC-II TOVA
Caregiver-reported assessments	CBCL HOME
Brain Powered Games	12th session for BPG training group and 1 session for wait list group 1 session at 6-months follow-up for entire sample

Table 4: 12 session trainings of Village Builder (wait-list) and

Component	Procedures
Administrative and	
 • Provide reimbursement for study visit
Clinical	
 • Obtain medical history • Conduct a brief physical examination (main organ systems and
Neurodevelopment Assessments	KABC-II TOVA
Caregiver-reported assessments	CBCL HOME
Village Builder	
 • Complete 12 sessions (About 2 per week for 6 weeks) of approximately 30-45 min

Table 5: Follow-up visits for wait-list group

Component	Procedures
Administrative and	
 • Provide reimbursement for study visit

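### The predictive-validity model leaves out the child's intake gold-standard score, so a positive BPG result would not show that BPG adds to existing testing

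*Combined protocol and SAP*

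**What the plan says.** Section 7.1.2 (Aims 1 and 2) evaluates predictive validity "in the LME model with the repeated gold standard measures at 1 and 7 months (6-month follow-up"). The covariate list begins "Covariates will include the BPG static measure at intake (baseline) and 1 month (post-training BPG; time-varying covariate), time (1 and 7 months") and ends with "other covariates (proximal and distal factors, Figure 1), and number of prior neuropsychological testing sessions". The intake gold-standard score is neither a covariate nor one of the repeated outcomes in this model.

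Other sections bear on the point:

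- Section 5.1: before any BPG session, "each child will return to the clinic with their principal caregiver for a half-day of gold standard neuropsychological assessments (KABC-II, TOVA, CogState"). The score will therefore be in hand.
- Section 4.1, on the value added by dynamic measures: "we used general linear models relating the KABC-II MPI post-training to the KABC-II MPI pre-training, and each dynamic performance measure".
- Section 2.0, central hypothesis: "the performance gains (dynamic assessment) will explain the additional variation in the gold-standard measures at time points after static (baseline) assessment".
- Section 5.6.6, Table 3, on the post-training BPG measure: "12th session for BPG training group and 1 session for wait list group".
- Section 5.6.5: "We will also use gain scores pre- to post-training for our gold standard of neuropsychological tests as our principal performance outcomes".

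**The concern.** A child who scores well on the KABC-II at intake will tend to score well at 1 and 7 months, and will tend to play BPG well. If the intake score is left out, a BPG coefficient can be significant only because BPG reflects the same baseline ability. A reader could then take the result as evidence that BPG tells us something the existing tests do not. That is the question the preliminary work asked, and it answered it with baseline MPI in the model.

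Three related matters are left open:

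- **One BPG term or two.** The text does not settle whether intake and 1-month BPG enter separately or as one switching time-varying term. If separately, the 1-month coefficient is already the coefficient for gain.
- **No arm term.** The 1-month measure is a twelfth session in one arm and a single repeat session in the other, but no training/wait-list term is listed.
- **Which outcome.** Section 5.6.5 names gold-standard gain scores as principal outcomes, whereas Section 7.1.2 models the scores themselves.

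**Working it through.** **Does anything else supply the intake score?** No.

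- Section 2.0 describes Figure 1 with the cognitive tests in the middle, apart from the proximal (HIV/ARV) and distal (risk-factor) covariates. The figure itself is not reproduced in the text reviewed.
- The number of earlier test sessions is a count, not a score.
- The Aim 3 model has intake gold-standard scores as outcomes, but no BPG predictor.

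**The plan's own figures.** No sample size or power is stated for this model. The figures in Section 7.1.2 concern known-groups comparisons: d = 0.26 at two-sided 0.05 and power 0.80 needs 233 per cohort, and 240 gives power 0.81. For d = 0.31 with 120 against 240, power is 0.79. These agree with the plan within rounding and do not depend on this point.

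**Inputs.** Table 1 of Section 4.1 has seven rows (Captain's Log, severe malaria survivors, N = 104). Correlations with baseline MPI (a) are 0.24–0.39; correlations with post-training MPI (b) are 0.32–0.47. The pre-post gold-standard correlation (c) is called strong but not given; I assume 0.5–0.8. The correlation between intake and 1-month BPG (ρ) is not given; I assume 0.5–0.9.

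**Step 1: share of the association left after adjustment.** Share = [(b − a·c)/(1 − a²)]/b. First row (a = 0.32, b = 0.37) at c = 0.7: (0.37 − 0.224)/(1 − 0.1024) = 0.163, and 0.163/0.37 = 0.44. Over all seven rows:

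- c = 0.5: 0.63–0.69
- c = 0.6: 0.54–0.59
- c = 0.7: 0.44–0.50
- c = 0.8: 0.34–0.42

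**Step 2: rejection when BPG adds nothing.** Suppose later scores depend on BPG only through the intake score. Each BPG term then correlates r = a·c with the outcome. The partial correlation of 1-month BPG given intake BPG is p = r·√[(1 − ρ)/(1 + ρ)]/√(1 − r²). Power follows from the noncentral t with noncentrality p√n/√(1 − p²).

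- Low end (a = 0.24, c = 0.5, ρ = 0.9): r = 0.12, p = 0.028; rejection 8% at n = 300 and 10% at n = 600.
- High end (a = 0.39, c = 0.8, ρ = 0.5): r = 0.312, p = 0.190; rejection about 91% at n = 300 and 99.7% at n = 600.

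**Step 3: simulation check** (2,500 replicates, c = 0.7, ρ = 0.6–0.8, a = 0.24–0.39), rejection rate for 1-month BPG:

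| Model | n = 300 | n = 600 |
|---|---|---|
| Intake and 1-month BPG only | 17–68% | 27–93% |
| Plus a covariate correlated 0.5 with baseline ability | 12–52% | 20–81% |
| Plus the intake score | 4.5–5.8% | 4.6–5.4% |

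A separate simulation, averaging the two follow-up visits and taking ρ = 0.3–0.7, gave 28–94% at n = 300, and about 4–6% with the intake score added.

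**Step 4: precision.** The residual SD with the intake score, relative to the BPG-only model, is √{(1 − c²)/[1 − 2r²/(1 + ρ)]}. At c = 0.5 it is 0.87–0.89; at c = 0.8 it is 0.61–0.64. That is a fall of 11–39%.

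**Step 5: the missing arm term.** Pool both arms (n = 600), put the intake score in the model, and assume no within-arm link. Suppose training shifts BPG by 0.5–1.0 SD and the gold standard by 0.1–0.3 SD. One-month BPG is then declared predictive in 8–82% of studies without an arm term and 4–6% with one.

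**The case against.** The best defence is that Section 7.1.2 promises predictive validity, and showing that an instrument predicts a later criterion does not require conditioning on the earlier criterion. BPG is justified largely as a cheaper substitute where the gold-standard tests are not available, and for that use the unadjusted prediction is the relevant quantity. This stands. The rejections in Steps 2 and 3 are not false positives for simple prediction, and the BPG-only model is worth keeping for that purpose.

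The central hypothesis can also be read as variation beyond BPG's own static score. With two separate BPG terms, the planned model does test that. But Section 4.1 defines added value with baseline MPI in the model, so the plan should say which claim it intends. The relative validity coefficients and standardized response means in Section 7.1.2 compare BPG with the gold standard, but they do not test incremental prediction.

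The gain-score wording in Section 5.6.5 does not rescue the model. It does not put the intake score into the Section 7.1.2 analysis. A gain outcome would also fix the intake coefficient at 1 instead of estimating it. With equal SDs and no added value, BPG would then have covariance a(c − 1) with gain, for example 0.32 × (0.7 − 1) = −0.096, so it would not give a clean test either.

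Finally, the ranges are wide, and they borrow correlations from another game package in another population. That is fair: they show the problem can be large, not how large it will be. The omission itself does not depend on them.

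**Conclusion.** The concern holds. As written, the model can describe whether BPG predicts later gold-standard scores, but it cannot show that BPG adds to the tests already given at intake. The figures rest on assumed pre-post and BPG correlations and on Table 1 of Section 4.1. Under them, 34–69% of the unadjusted association would survive adjustment, and with no added value 1-month BPG would be significant in 8–91% of studies at n = 300, against about 5% with the intake score in the model.

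The consequence is bounded. The primary outcome in Section 5.3 is a set of correlations, and neither it nor the sample size uses this model. All seven measures in Table 1 of Section 4.1 stayed associated with post-training MPI after baseline adjustment (p = .04 or smaller), so the adjusted test is workable. This should be clarified before analysis.

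**What to change.** In Section 7.1.2:

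- Add the intake value of the same gold-standard measure as a covariate in each predictive mixed model. If wanted, keep the BPG-only model as a secondary description of simple prediction.
- State that intake BPG and 1-month BPG (equivalently, intake BPG and gain) enter together as two separate terms.
- Add a training/wait-list term, or test gain within the trained arm.
- State how the gain-score outcomes of Section 5.6.5 relate to the outcomes of this model.

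The cost is a few sentences and no new data. There are four drawbacks:

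- The apparent BPG association will be smaller.
- A test confined to the trained arm uses 300 of the 600 children.
- A child without an intake score leaves the adjusted model unless missing data are handled.
- Measurement error in the intake score means adjustment reduces the problem but may not remove it. At n = 300 the adjusted model rejects in 7–17% of studies at an assumed reliability of 0.8, and in 5–8% at 0.9.
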